## 8. ANALYSIS DETAILS

The results of the analyses will be reported following the principles of the ICH E3 guidelines on the Structure and Content of Clinical Study Reports.

### 8.1 Recruitment and follow-up patterns

- Screening, patient enrolment, treatment allocation, withdrawals, follow-up and inclusion in primary analysis will be reported using CONSORT diagram
- The numbers of exclusion will be summarized based on the exclusion and inclusion criteria

### 8.2 Baseline Characteristics

- Gender, n(%) by treatment arm
- Age(years), mean(SD) by treatment arm
- Height(m), mean(SD) by treatment arm
- Weight(kg), mean(SD) by treatment arm
- BMI(kg/m^2), mean(SD) by treatment arm
- Transfer Factor((TLCO) as a percentage of the predicted value(%)), mean(SD) by treatment arm
- Forced Expiratory Volume(FEV1 (L)), mean(SD) by treatment arm
- Forced Vital Capacity(FVC (L)), mean(SD) by treatment arm
- FEV1/FVC Ratio (%), mean(SD) by treatment arm
- Mid Expiratory Flow (MMEF 25-75% (L/s)), mean(SD) by treatment arm
- Peak Expiratory Flow(PEF (L/s)), mean(SD) by treatment arm
- Smoking Status, n(%) by treatment arm
- Pack Years, mean(SD) by treatment arm
- Presence of EBV, n(%) by treatment arm
- Quantitative PCR Titre(copies), mean(SD) by treatment arm
- Co-morbidities, n(%) by treatment arm
- Pre-existing Cardiovascular issues, n(%) by treatment arm
- Any exacerbations in past 12 months, n(%) by treatment arm

- Number of exacerbations in past 12 months, n(%) by treatment arm
- Number of exacerbations in past 12 months requiring steroids, n(%) by treatment arm
- Number of exacerbations in past 12 months requiring antibiotics, n(%) by treatment arm
- Number of exacerbations in past 12 months resulting in hospitalization, n(%) by treatment arm

### 8.3 Trial treatment

- Number of patients receiving at least one unit/dose of the drug, n(%) by treatment arm
- Duration of study drug (days), mean(SD) by treatment arm
- Overall compliance, mean(SD) by treatment arm
- Compliance, n(%) by treatment arm
- Time lapse between randomisation and study drug administration, mean(SD) by treatment arm
- Reason for study drug termination, n(%) by treatment arm
- Protocol Deviations/Violations, n(%) by treatment arm
- Premature withdrawals, n(%) by treatment arm

### 8.4 Trial Outcomes

- **Primary Safety Outcome**
  - Incidence of serious adverse reactions (SARs) Serious adverse reaction, n(%) by treatment group, Relative risk 95% CI
- **Primary Efficacy Outcome**
  - Suppression of Epstein-Barr virus in the sputum of subjects with COPD from baseline to week 8
    - Number of patients experiencing suppression of Epstein-Barr virus, n(%) by treatment arm, odds ratio and 95% CI (Note: Suppression as defined by a 90% reduction in Quantitative PCR at week 8 when compared to baseline) followed by logistic

- regression adjusting for FEV1 and other covariates if required at baseline.
  - Descriptive results for sputum sample including; presence of EBV (yes/no) at baseline, week 4 and week 8, n(%) by treatment arm
- Change in viral load (Quantitative PCR) from baseline to week 8, mean(SD) by treatment arm, difference in mean with 95% CI\*
  - Descriptive results for quantitative PCR Titer(copies) at baseline, week 4 and week 8, mean(SD) by treatment arm
- Subgroup Analyses\*
  - Compliance ( $\geq 80\%$ , 60-79%,  $< 60\%$ ), n(%) by treatment arm, odds ratio and 99% CI from the treatment\*subgroup interaction model
- Sensitivity Analyses \*
  - Sensitivity analysis will be performed for the primary outcome excluding patients with a confirmed diagnosis of COVID-19 reported as an adverse event.
- **Secondary Outcomes**
  - **Lung function**
    - Change in FEV1 from baseline to week 8, mean(SD) by treatment arm, difference in mean with 95% CI
      - Exploratory Subgroup Analysis\*: EBV Suppression (as defined by 90% reduction in viral load) (Yes, No), mean(SD) by treatment arm, difference in mean and interaction term from ancova with 99% CI
    - Change in Forced Expiratory Volume in 1 second (FEV1 as a percentage of the predicted FEV1 value (%)) from baseline to week 8, mean(SD) by treatment arm, difference in mean with 95% CI
      - Exploratory Subgroup Analysis\*: EBV Suppression (as defined by 90% reduction in viral load) (Yes, No),

- mean(SD) by treatment arm, difference in mean and interaction term from ancova with 99% CI
- Change in FVC from baseline to week 8, mean(SD) by treatment arm, difference in mean with 95% CI
    - Exploratory Subgroup Analysis\*: EBV Suppression (as defined by 90% reduction in viral load) (Yes, No), mean(SD) by treatment arm, difference in mean and interaction term from ancova with 99% CI
  - Change in FEV1/FVC ratio from baseline to week 8, mean(SD) by treatment arm, difference in mean with 95% CI
    - Exploratory Subgroup Analysis\*: EBV Suppression (as defined by 90% reduction in viral load) (Yes, No), mean(SD) by treatment arm, difference in mean and interaction term from ancova with 99% CI
  - Change in MMEF from baseline to week 8, mean(SD) by treatment arm, difference in mean with 95% CI
    - Exploratory Subgroup Analysis\*: EBV Suppression (as defined by 90% reduction in viral load) (Yes, No), mean(SD) by treatment arm, difference in mean and interaction term from ancova with 99% CI
  - Change in PEF from baseline to week 8, mean (SD) by treatment arm, difference in mean with 95% CI
    - Exploratory Subgroup Analysis\*: EBV Suppression (as defined by 90% reduction in viral load) (Yes, No), mean(SD) by treatment arm, difference in mean and interaction term from ancova with 99% CI
  - Exploratory Subgroup Analysis\*: EBV Suppression (as defined by 90% reduction in viral load) (Yes, No), mean(SD) by treatment arm, difference in mean and interaction term from ancova with 99% CI
  - Change in TLCO from baseline to week 8, mean(SD) by treatment arm, difference in mean with 95% CI

- Exploratory Subgroup Analysis\*: EBV Suppression (as defined by 90% reduction in viral load) (Yes, No), mean(SD) by treatment arm, difference in mean and interaction term from ancova with 99% CI
  - Descriptive statistics for lung function including; FEV1, FEV1 as a percentage of the predicted FEV1 value, FVC, FEV1/FVC Ratio, MMEF, PEF and TLCO at baseline, week 4 and week 8, mean(SD) or median (IQR) by treatment arm.
  - Difference between lung function measures at baseline and week 8 in the active and placebo groups separately for all lung function outcomes, mean (SD) within each treatment arm, mean difference and 95% CI
- Participant compliance measured by total number of tablets administered as a proportion of total number of tablets supplied, mean(SD) by treatment arm, mean difference and 95% CI
- **Exploratory Outcomes**
  - Clinical
    - Symptoms measured by CAT score and EQ-5D-5L from baseline to week 8, n(%) by treatment arm, mean difference and 95% CI
      - Descriptive statistics will also be presented at baseline, week 4 and week 8, mean(SD), median (IQR) or n(%) by treatment arm.
    - Suppression of Epstein-Barr virus in the sputum of subjects with COPD from baseline to week 4, n(%) by treatment arm, odds ratio and 95% CI\*
    - Number of exacerbations reported between baseline and week 12, mean(SD) by treatment arm, mean difference and 95% CI \*

\*Not detailed in study protocol

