### 10.1.5 Follow Up (Week 12 +/- 7 days) Procedures

For those patients who withdraw from the trial / discontinue the study drug prior to 8 weeks or following the completion of 8 weeks of treatment, the CI or designee will contact the patient by telephone 4 weeks post study drug termination to assess if the patient is experiencing any adverse events. Participants will be asked regarding exacerbation status and if applicable exacerbations will be documented.

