## **13 STATISTICAL CONSIDERATIONS**

### 13.1 Sample Size

A sample size of 31 subjects per group will have 90% power at a two-tailed significance level of 0.05 to detect a difference in the primary efficacy outcome EBV shedding of 70% in the treated group to 30% in the control group. With a dropout rate of approximately 30%, this study will require a total of 44 patients per group.

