## 5. SAMPLE SIZE CALCULATIONS

A sample size of 31 subjects per group will have 90% power at a two-tailed significance level of 0.05 to detect a difference in the exploratory efficacy outcome EBV shedding of 70% in the treated group to 30% in the control group. With a dropout rate of approximately 30%, this study will require a total of 44 patients per group.

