## **7. ANALYSIS PRINCIPLES**

The comparison of continuous outcomes will be carried out using t-tests followed by analysis of covariance adjusting for baseline FEV1 and other covariates if required. The mean and 95% confidence intervals will be reported. The categorical variables will be analysed using Fisher's Exact test or Chi-square test followed by logistic regression adjusting for baseline FEV1 and other covariates if required. The odds ratio and 95% confidence will be reported.

Statistical diagnostic methods will be used to check for violations of the assumptions, and transformations will be performed where required. Analyses will be on an intention-to-treat basis and all statistical tests will be at the 2-sided p-value of 0.05. A single final analysis is planned at the end of the trial.

Every effort will be made to minimise missing baseline and outcome data in this trial. The level and pattern of the missing data in the baseline variables and outcomes will be established by forming appropriate tables and the likely causes of any missingness will be investigated. This information will be used to determine whether the level and type of missing data has the potential to introduce bias into the analysis results for the proposed statistical methods, or substantially reduce the precision of estimates related to treatment effects. If necessary, these issues will be dealt with using multiple imputation or Bayesian methods for missing data as appropriate.

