**Table x.x Exploratory Outcomes**

	All patients	Valaciclovir	Placebo	Difference (95% CI)	p-value
CAT Score	xx.x (x.x)	xx.x (x.x)	xx.x (x.x)	xx.x (x.x to x.x)	0.xxx
EQ-5D-5L	xx.x (x.x)	xx.x (x.x)	xx.x (x.x)	xx.x (x.x to x.x)	0.xxx
Suppression of Epstein-Barr virus in the sputum of subjects with COPD from baseline to week 4*	N(%)	N(%)	N(%)	xx.x (xx.x – xx.x)	0.xx
Number of exacerbations reported between baseline and week 12	xx.x (x.x)	xx.x (x.x)	xx.x (x.x)	xx.x (x.x to x.x)	0.xxx

Continuous outcomes reported as Mean (SD) (or median(IQR) if appropriate). Categorical outcomes reported as n(%).

\*odds ratio and 95% CI presented

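### The exploratory comparison of exacerbation counts to week 12 ignores time observed, so it is modestly biased if dropout differs between arms

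*SAP*

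**What the plan says.** SAP 8.4, under clinical exploratory outcomes, lists "Number of exacerbations reported between baseline and week 12, mean(SD) by treatment arm, mean difference and 95% CI". It marks the item as not detailed in the protocol. The Exploratory Outcomes table in Appendix 1 repeats "Number of exacerbations reported between baseline and week 12" with a difference, 95% CI and p-value. Its footnote reads "Continuous outcomes reported as Mean (SD) (or median(IQR) if appropriate" and has no place for time observed. SAP 7 gives the general method: "The comparison of continuous outcomes will be carried out using t-tests followed by analysis of covariance", adjusted for baseline FEV1 and other covariates if required. Neither document names a count model, an offset or an event rate.

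Four provisions bear on how long each patient is observed:

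- SAP 5 and Protocol 13.1 inflate the sample size for dropout ("With a dropout rate of approximately 30" per cent).
- Protocol 7.3 keeps data recorded up to withdrawal. It also says that patients who only stop the drug stay in follow-up.
- Protocol 10.1.5 sets the closing call 4 weeks after the drug is stopped, also for those who stop or withdraw before week 8. At that call, "Participants will be asked regarding exacerbation status and if applicable exacerbations will be documented".
- SAP 3.4 says missing clinical data will not be imputed, while SAP 7 allows multiple imputation or Bayesian methods if necessary. Neither says what to do with a count that covers only part of the 12 weeks.

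**The concern.** A count is comparable between patients only if they were watched for the same time. Under the plan as written, a patient who stops at week 2, is called at about week 6 and has had no event contributes the same zero as a patient followed to week 12. The same holds for a median or a rank test, so the footnote's alternative does not help. If one arm loses more patients, its mean count falls for that reason alone.

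At stake is how a small part of the report is read. This is the only dedicated between-arm comparison of exacerbations. Protocol 12.8 says adverse events associated with the underlying condition should not be reported, so exacerbations may be largely absent from the adverse event tables. Week 8 spirometry was dropped under the COVID-19 amendment. The result will carry a confidence interval and a p-value, so readers will interpret it.

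**Working it through.** **Inputs from the documents.** Protocol 13.1: "A sample size of 31 subjects per group will have 90% power at a two-tailed significance level of 0.05 to detect a difference", for "EBV shedding of 70% in the treated group to 30% in the control group", raised to 44 per group for about 30% dropout. The nominal window is 12 weeks. The last call comes 4 weeks after stopping drug.

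**The plan's own figure.** With pooled variance and no continuity correction, n = [1.96·√(2·0.5·0.5) + 1.282·√(0.21 + 0.21)]² / 0.4² = 30.7, so 31 per group (power 90.3%). Then 31/0.7 = 44.3, against 44 stated. The figure reproduces, within rounding. It concerns sputum EBV; the documents give no figure for exacerbations.

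**Assumed, not in the documents.** No true effect; dropout unrelated to exacerbation risk; 0.5 exacerbations per patient per 12 weeks; gamma-Poisson counts with dispersion 1; dropout split 40% v 20% or 45% v 15%, both averaging 30%.

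**Expected share of the 12 weeks observed, with dropout proportion d:**

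- Call made: drug stops uniformly over weeks 0–8 and the last contact is 4 weeks later, so dropouts are seen for 8 weeks on average. Share = 1 − d/3.
- Lost at once, uniformly over weeks 0–12 (mean 6 weeks). Share = 1 − d/2.
- Lost at once, uniformly over weeks 0–8 (mean 4 weeks). Share = 1 − 2d/3.

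With no true effect, the ratio of raw means is the ratio of these shares, and the shift in the mean is 0.5 times their difference.

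| Follow-up of dropouts | Dropout | Shares | Ratio of raw means | Shift, events per patient |
|---|---|---|---|---|
| Call made | 40% v 20% | 0.867 / 0.933 | 0.93 | −0.03 |
| Call made | 45% v 15% | 0.85 / 0.95 | 0.895 | −0.05 |
| Lost, weeks 0–12 | 40% v 20% | 0.80 / 0.90 | 0.89 | −0.05 |
| Lost, weeks 0–12 | 45% v 15% | 0.775 / 0.925 | 0.84 | −0.075 |
| Lost, weeks 0–8 | 40% v 20% | 0.733 / 0.867 | 0.85 | −0.07 |
| Lost, weeks 0–8 | 45% v 15% | 0.70 / 0.90 | 0.78 | −0.10 |

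With 30% dropout in both arms the ratio is 1.00 in every row.

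**Against sampling error.** At full follow-up the variance of a count is 0.5 + 0.5² = 0.75. The standard error of the difference is then √(2·0.75/44) = 0.18, and a little less once follow-up is truncated. The shifts above are well inside it.

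**Simulation, 44 per arm.** The raw ratios match the table. Events divided by person-time give 0.99 to 1.01 in every setting. At 0.5 events per 12 weeks, the t-test rejects a true null in about 5% (40% v 20%) to about 6% (45% v 15%) of trials when the call is made. When dropouts are lost at once it rejects in about 6 to 7% and 7 to 9%. At lower event rates the excess is smaller.

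**The case against.** The strongest reply is that the documents already limit the problem. Patients who only stop the drug remain in follow-up, and access to records is sought after consent is withdrawn (Protocol 7.3). The remaining visits are by telephone with review of online health records (amendment summary before Protocol Table 2). The 30% is an allowance for the sputum endpoint, not an estimate of lost exacerbation contact. SAP 3.4 expects little missing data, and SAP 7 requires its pattern to be examined. The outcome is exploratory, and no primary or secondary conclusion depends on it. All of this stands, and it is why the call-made rows are the more relevant ones. It does not supply a rule for the patients whose window is still short.

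A second reply is that the error rate does not favour a rate model at this size. In 1,500 simulated trials at 40% v 20% with the call made, robust Poisson rejected in 6.8% and negative binomial in 6.3%, against 5.1% for the t-test. The negative binomial and Poisson fits failed to converge in 2 to 5% of trials across settings. The Monte Carlo error is about 1 point. That also stands: the case for the change is bias in the estimate, not control of false positives.

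A reader might infer three stronger points that the documents do not support:

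- That 30% dropout by itself biases the comparison. It does so only if the loss differs between arms, and no figure by arm is given.
- That this is the only between-arm look at COPD worsening. The change in CAT to week 8 is also compared (SAP 7.2 and 8.4).
- That the direction is fixed. If patients leave because they exacerbate, it can change.

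**Conclusion.** The point holds as a minor one. The plan compares raw counts over a nominal 12 weeks although follow-up can be shorter for some patients, and nothing in either document corrects for that. Under the stated assumptions, unequal dropout makes the arm with more loss look about 7 to 10% better if the 4-week call is made, and about 11 to 22% better if dropouts vanish at once. In absolute terms that is 0.03 to 0.10 events per patient, against a standard error of about 0.17 to 0.18. Someone might read the larger figures as the expected effect, or as a serious inflation of the false-positive rate. They apply only if dropouts also miss the call that Protocol 10.1.5 schedules, and even then rejection stays below 10%. The dropout splits and the event rate are assumptions; with equal dropout there is no bias at a true null. The harm is a modestly biased estimate in an exploratory outcome.

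**What to change.** In SAP 8.4 and the Exploratory Outcomes table, replace the mean difference with negative binomial regression, or Poisson regression with robust standard errors if that does not converge. Use as offset the log of time from randomisation to the last exacerbation contact or record review. Report the rate ratio with 95% CI, and the events and person-time in each arm. State when counting ends for a patient who stops or withdraws early, and reconcile SAP 3.4 with SAP 7 on imputation.

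The cost is SAP wording and a few lines of code. Exacerbation status is already asked at every scheduled contact, so no new question is needed. The CRF is not among the documents, so confirm that it holds the date of the last contact or record review. The downsides are that a rate ratio is less direct to read than a mean difference, that standard errors are approximate at 44 per arm, and that an offset does not cure dropout caused by exacerbations.

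### The exploratory week-12 exacerbation comparison does not commit to adjusting for the prior-year exacerbation count, giving up a modest amount of precision

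*SAP*

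**What the plan says.** SAP 8.4 lists, among the exploratory clinical outcomes, "Number of exacerbations reported between baseline and week 12, mean(SD) by treatment arm, mean difference and 95% CI". A footnote marks it as "Not detailed in study protocol". The Exploratory Outcomes table in Appendix 1 keeps the same layout and adds a p-value. Its note reads "Continuous outcomes reported as Mean (SD) (or median(IQR) if appropriate", so the count is handled as a continuous variable. SAP 7.2 gives methods for lung function, compliance, CAT and EQ-5D, but none for exacerbations.

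Exacerbation history appears in SAP 8.2 as "Number of exacerbations in past 12 months, n(%) by treatment arm", next to the numbers needing steroids, antibiotics or hospital admission. The baseline table in Appendix 1 repeats these items. No analysis section uses them.

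The general rule in SAP 7 is a t-test followed by "analysis of covariance adjusting for baseline FEV1 and other covariates if required". Protocol 13.2 has a similar open allowance for secondary and exploratory outcomes. Neither names exacerbation history or says when adjustment is called for. Protocol 8.1 and SAP 6.1 describe 1:1 allocation and mention no stratification on it.

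**The concern.** For a count of exacerbations, the patient's own count over the preceding year is the nearest thing to a baseline value of the outcome. It is a more natural covariate than FEV1, the only one the SAP names. The described design does not balance it and the analysis does not commit to adjusting for it.

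Two things follow. First, between-patient variation that the baseline count could explain stays in the error term. Second, if one arm happens to receive more frequent exacerbators, part of that difference carries into the estimate. Because the SAP names no covariate and no trigger, whether to adjust could also be settled after the data are seen. Lung function is no longer measured, so exacerbations, with CAT and EQ-5D-5L, are among the few patient-relevant outcomes still collected.

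**Working it through.** **The plan's own figure.** SAP 5 states "A sample size of 31 subjects per group will have 90% power at a two-tailed significance level of 0.05", for "EBV shedding of 70% in the treated group to 30% in the control group". With the pooled-variance formula, n = (1.96·√(2·0.5·0.5) + 1.2816·√(0.21 + 0.21))² / 0.4² = (1.386 + 0.831)² / 0.16 = 30.7, so 31 per group, with power 90.3%. Allowing for 30% dropout, 31 / 0.7 = 44.3, against the stated 44. The figure reproduces, but it concerns EBV. Nothing in the documents sizes the exacerbation comparison.

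**Inputs for exacerbations.** The documents supply 44 per arm, a 12-week window, and a two-sided 0.05 level ("all statistical tests will be at the 2-sided p-value of 0.05"). They give no exacerbation rate or dispersion, so these are assumptions: a rate m of 1 to 2 per patient-year and a between-patient gamma variance v of 0.3 to 1.0. Expected events per arm are then 44 × 12/52 × 1 = 10.2 to 44 × 12/52 × 2 = 20.3, or 7.2 to 14.3 with 31 evaluable.

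**Model.** Each patient has one underlying rate, shared by the prior year and the 12 weeks. With l = m × 12/52 and equal rates in both arms:

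- variance of the prior-year count = m + v·m²; variance of the 12-week count = l + v·l²; covariance = v·m·l
- r = v·m·l / √[(m + v·m²)(l + v·l²)]
- SE ratio after linear adjustment = √(1 − r²); equivalent extra patients = 1/(1 − r²) − 1
- slope b = v·l / (1 + v·m); an imbalance of 0.5 prior-year exacerbations per patient shifts the unadjusted difference by 0.5·b

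Low end (m = 1, v = 0.3): l = 0.231, covariance 0.069, variances 1.3 and 0.247, so r = 0.069 / √(1.3 × 0.247) = 0.122. High end (m = 2, v = 1.0): l = 0.462, covariance 0.923, variances 6 and 0.675, so r = 0.923 / √(6 × 0.675) = 0.459.

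| m | v | r | r² | SE smaller by | Equivalent extra patients | Shift from 0.5 imbalance (in SEs, 44 per arm) |
|---|---|---|---|---|---|---|
| 1 | 0.3 | 0.122 | 0.015 | 0.7% | 1.5% | 0.027 (0.25) |
| 1 | 0.5 | 0.186 | 0.034 | 1.7% | 3.6% | 0.038 (0.36) |
| 1 | 1.0 | 0.306 | 0.094 | 4.8% | 10.3% | 0.058 (0.51) |
| 2 | 0.3 | 0.214 | 0.046 | 2.3% | 4.8% | 0.043 (0.28) |
| 2 | 0.5 | 0.306 | 0.094 | 4.8% | 10.3% | 0.058 (0.36) |
| 2 | 1.0 | 0.459 | 0.211 | 11.1% | 26.7% | 0.077 (0.44) |

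An imbalance of 0.5 is 0.5 / √(2 × 1.3/44) = 2.1 SE of the prior-year difference at the low end, and 0.5 / √(2 × 6/44) = 1.0 SE at the high end. Widening the rate to 0.5 to 3 per year widens the SE reduction to 0.2% to 17%.

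**Simulation check** (m = 1 and 2, v = 0.5 and 1.0; 44 per arm; unadjusted comparison against ANCOVA on the prior-year count; 6,000 null trials and 3,000 trials with a halved rate per scenario):

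- SE ratios of 0.987, 0.952, 0.955 and 0.882, in line with the formula.
- Type I error over all trials: unadjusted 4.6% to 5.7%, adjusted 4.9% to 5.5%.
- Type I error where the prior-year imbalance exceeds 1.5 SE: unadjusted 5.3% to 13.6%, adjusted 3.1% to 5.9%. About 13% of trials, some 800 per scenario, meet this condition, so each figure has a simulation error near 0.8 percentage points.
- Power for a halved rate: at 1 per year, 22.5% to 22.6% and 22.2% to 21.3% on adjusting; at 2 per year, 38.9% to 40.5% and 34.4% to 38.3%.

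**The case against.** The strongest reply is that the plan already allows this. SAP 7 leaves room for further covariates, and Protocol 13.2 for other suitable methods. A reader might therefore infer too much in saying that the plan ignores exacerbation history: adjustment is permitted, and what is missing is a commitment. That stands. It does not close the gap, because an unnamed covariate with no trigger is not prespecified.

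A reader might also infer that any imbalance passes whole into the result, or that the planned test is invalid. Neither holds. Only the slope-carried part passes, 0.027 to 0.077 events for an imbalance of 0.5. The unadjusted test keeps its error near 5% over all randomisations; the higher error appears only in trials selected for marked imbalance.

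The gain rests wholly on assumed rates, and at 1 per year it has no visible effect on power. The shared-rate model may overstate the correlation, because patients with an exacerbation in the previous month are excluded. Both points stand.

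Finally, a reader might infer that the mean difference must give way to a count model. The covariate argument does not require that. A count model would normally change the effect measure to a rate ratio, and about 7 to 20 events per arm is thin for estimating dispersion as well.

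**Conclusion.** The point holds as a small improvement to an exploratory analysis. The SAP does not commit the week-12 exacerbation comparison to the most relevant baseline variable it lists. At 1 to 2 exacerbations per year and variance 0.3 to 1.0, the loss is about 2% to 21% of outcome variance, or an SE about 1% to 11% larger than it need be, together with weaker protection when the arms happen to differ in exacerbation history. These figures depend on the assumed rates and on a patient's rate being stable across both periods. The planned comparison is not biased, and no primary or secondary conclusion rests on it.

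**What to change.** In SAP 8.4 and the Exploratory Outcomes table, prespecify the between-arm mean difference and 95% CI adjusted for the prior-year exacerbation count, for example by ANCOVA with robust standard errors. State the coding in advance: 0 / 1 / 2 or more, or log(count + 1). Either limits the pull of a few very high counts. Under the model above the expected 12-week count is linear in the raw prior-year count, so a recoded version recovers at most the gain shown. Code patients recorded as having no exacerbations as 0, since the Appendix 1 baseline table gives the number only for those with any. Keep the unadjusted means by arm as description. A count model is optional.

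The cost is one sentence in the SAP, a table note, and one or two degrees of freedom. No new data should be needed: the SAP already lists the count as a baseline characteristic. The CRF is not among the documents, so confirm there that the count is recorded before randomisation for every patient.
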